## Test methods

### *Water-Immersion Wrinkle Test (WIWT):*

Technique: Patients will be seated upright with both hands immersed in water in a comfortable position. The proposed immersion time will be 15 minutes and the temperature will be maintained at 40 °C, verified with a thermometer available in the service. Cutaneous wrinkles will be graded using a published and validated scale.[27] Wrinkles will be considered abnormal if absent or severely reduced (Grades 0–2).

Wrinkle grading scale:

- Grade 0: Absence of wrinkles.
- Grade 1: Barely perceptible wrinkles with the fingertip not completely smooth.

- Grade 2: Two or fewer superficial wrinkle lines on the fingertip.
- Grade 3: Three or more deep wrinkle lines on the fingertip.
- Grade 4: Wrinkles that completely distort the fingertip pulp.

Data collection and assessment: Wrinkles will be evaluated at all times by a trained examiner. The examiner will assign the rating at the end of the test and will be blinded to QST and SSR results. The examiner's final result will be the sum of grades for digits 2, 3, 4, and 5. Using 12 points as the threshold (Grades 3 and 4 considered normal), a score equal to 12 points (3 points per finger) is the lower limit of normal. Scores below 12 points will be considered abnormal. Both hands will be assessed and the scores summed, using 24 points as the lower limit of normal.

Inter- and intra-observer variability of the wrinkle score will be assessed using four investigators trained in wrinkle assessment, who will receive photographs of subjects with different degrees of wrinkling. Photographs of the fingertips will be taken with the rear camera of an iPhone 13 (12 MP), at a distance of 10 cm and with a black background, set to  $3024 \times 4032$  pixels and saved in JPEG format. In each test session, the images will be arranged in random order and distributed to the investigators, who will evaluate the digital photos. Each rater will score the same group of photos on two different days. The minimum time between assessments will be 48 hours and the maximum 7 days. Grades for digits 2, 3, 4, and 5 of both hands will be summed, and the normal/abnormal thresholds defined above will be used.

*Quantitative Sensory Testing (QST):*

Assessment areas: all four limbs are tested. For thermal threshold detection, four attempts are taken and averaged. For vibratory threshold detection, six attempts are taken and averaged. Routine selected areas include:

- Thenar eminence of both hands (for thermal thresholds)
- Dorsal aspect of both feet (for thermal thresholds)
- Palmar surface of the distal phalanx of the index finger of both hands (for vibratory thresholds)
- Plantar surface of the first metatarsophalangeal joint (for vibratory thresholds)

Determination of thermal thresholds: A device delivering controlled thermal stimuli is used, such as the Medoc™ Thermal Sensory Analyzer (TSA-II), which has a contact probe ( $30 \times 30$  mm) to measure thermal perception thresholds. Stimuli are administered with a controlled increase or decrease in temperature at a rate of  $1^{\circ}\text{C}/\text{s}$ , starting from a baseline temperature of  $32^{\circ}\text{C}$ . Maximum and minimum temperatures evaluated are  $50^{\circ}\text{C}$  and  $16^{\circ}\text{C}$ , respectively. The following parameters are evaluated:

- Warm detection threshold (WDT): the temperature at which the patient perceives the onset of a change toward warmth.

- Cold detection threshold (CDT): the temperature at which the patient perceives the onset of a change toward cold.

The method of limits is used to determine these thresholds, asking the patient to indicate the exact moment at which a change in temperature is perceived or pain appears.

In the QST protocol, vibration testing is performed to measure the vibration perception threshold. This test is performed with a Medoc™ Vibration Sensory Analyzer (VSA-3000).

**Procedure:** The device generates vibration at a controlled frequency. The patient indicates when the vibratory stimulus is felt and when it disappears. **Criteria:** Vibration is considered abnormal when thresholds exceed normative reference values ( $Z > +1.96$  or  $Z < -1.96$ ).

#### *Sympathetic Skin Response (SSR):*

The patient must be at rest and in a warm environment to avoid vasoconstriction that may alter results. The skin must be clean and free of oils or creams. Surface electrodes are placed on the skin in the area of interest, typically on the palm of the hand or the sole of the foot. Surface electrodes with conductive gel are used to ensure good conductivity. A series of brief, low-intensity electrical stimuli is applied to a specific nerve to elicit a sudomotor response. Stimulation is performed at standardized frequency and duration. The change in voltage on the skin surface is recorded before, during, and after stimulation. Electromyography (EMG) recording equipment is used. A surface electrode on the left palm with a reference electrode on the dorsum is standardized. Data are analyzed to determine the amplitude and latency of the sympathetic skin response and compared with reference values. These are:

- Stimulus intensity: 19.5 mA
- Latency: < 1800 ms
- Amplitude: > 900  $\mu$ V

## **Statistical analysis**

The diagnostic tests used for the detection of SFN will be compared, focusing primarily on WIWT and comparing its accuracy against QST and SSR in patients with and without neuropathy. The reference standard will be a combination of neurological assessments and validated quantitative scales (UENS and mTCNS). Statistical methods for evaluating diagnostic accuracy will be conducted in accordance with the STARD (Standards for Reporting of Diagnostic Accuracy) guidelines.[40]

#### **Analysis objectives**

- Compare the sensitivity and specificity of WIWT versus QST and SSR.
- Evaluate intra- and inter-observer correlation for WIWT reproducibility.
- Estimate diagnostic performance (accuracy) of each test compared against the reference standard using the area under the ROC curve (AUC).

## Statistical methods

Nonparametric tests (such as Mann–Whitney) or the unpaired t-test, as appropriate, will be used to compare scores obtained in the different diagnostic tests between patients with and without SFN. Mann–Whitney U will be used when the data are not normally distributed (assessed using normality tests such as Shapiro–Wilk), and the unpaired t-test will be used when the data are normally distributed. A two-sided p value  $< 0.05$  will be considered statistically significant.

The diagnostic accuracy of WIWT, QST, and SSR will be evaluated using the area under the ROC curve (AUC). The following metrics will be calculated:

Sensitivity: proportion of true positives.

Specificity: proportion of true negatives.

Positive Predictive Value (PPV) and Negative Predictive Value (NPV): estimated to provide additional evaluation of clinical performance.

Intra- and inter-observer correlation for WIWT will be calculated using the intraclass correlation coefficient (ICC) to assess reproducibility of ratings between different observers and within the same observer at different times.

Data will be recorded in Microsoft Excel® 2016 and analyzed with StatsDirect® Statistical Analysis.

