## Secondary Objectives

1. To estimate the ROC area under the curve (AUC) of the continuous WIWT score versus the composite reference at baseline.
2. To estimate positive and negative predictive values for WIWT at the observed SFN prevalence at baseline.
3. To assess inter-rater reliability of WIWT wrinkle scoring using ICC(2,1), with two rating sessions 48 hours to 7 days apart.
4. To assess intra-rater reliability of WIWT wrinkle scoring using ICC(3,1), with a second reading 48 hours to 7 days later.
5. To compare diagnostic performance of WIWT with QST and SSR at baseline, including AUC and sensitivity/specificity.

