## **Selection criteria**

### *Inclusion*

- Age > 18 years.
- Suspicion of small-fiber neuropathy based on history and/or physical examination by a neuromuscular neurology specialist.
- Sensory and motor nerve conduction studies within normal limits.
- Prior QST performed, regardless of result.
- Prior SSR performed, regardless of result.

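### Secondary objective 5 compares WIWT with QST and SSR in the same patients, but the plan gives no measure of uncertainty for the between-test difference

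*Combined protocol and SAP*

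**What the plan says.** The comparison appears in three places:

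- Secondary Objectives, item 5: "To compare diagnostic performance of WIWT with QST and SSR at baseline, including AUC and sensitivity/specificity".
- Statistical analysis: the focus is on WIWT, "comparing its accuracy against QST and SSR in patients with and without neuropathy".
- Analysis objectives, first item: "Compare the sensitivity and specificity of WIWT versus QST and SSR".

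The design is paired. The inclusion criteria require "Prior QST performed, regardless of result" and "Prior SSR performed, regardless of result", and Definition and operationalization of variables says that included patients are offered WIWT. Each patient is therefore expected to have all three results.

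Statistical methods then provides two things. One is a Mann-Whitney or unpaired t-test, which "will be used to compare scores obtained in the different diagnostic tests between patients with and without SFN". The other is a set of accuracy measures for each test: AUC, sensitivity, specificity and the predictive values. It names no paired method and no confidence interval. The only general statement is in Statistical analysis: "Statistical methods for evaluating diagnostic accuracy will be conducted in accordance with the STARD" guideline. That sentence names no method for comparing two tests. The reference list has an entry on two-part statistics with paired data and one on ROC curves, but the analysis sections name no method from either.

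**The concern.** Followed as written, the plan answers a stated objective with side-by-side point estimates from about 30 patients. When two tests are applied to the same patients, the precision of their difference depends on how many patients are positive on one test and negative on the other. Two separate sensitivities do not show this. Nor can a reader recover it from separate confidence intervals, if those were added. The risk is over-reading in either direction: similar percentages taken as evidence that WIWT performs like QST or SSR, or different percentages taken as evidence that one test is better.

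**Working it through.** The documents state no figure for the between-test comparison, so there is nothing to reproduce. The check asks how far the interval for a difference can vary when the two separate estimates are held fixed.

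**Inputs**
- About 30 subjects in total (Sample size).
- Sensitivity 80% (Sample size, from the literature; taken here as WIWT).
- QST sensitivity 60–85% (Introduction). No sensitivity is given for SSR.
- Number of reference-positive patients: not given. Assumed 15, with 10 and 30 as the range.
- Agreement between tests: not given. All tables with non-negative association are considered.

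**Method.** Newcombe's paired score interval, without continuity correction. Write the table among reference-positives as (both positive *a*, WIWT only *b*, other only *c*, both negative *d*), with D = p1 − p2 and Wilson 95% limits (l, u) for each proportion:

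- φ = (ad − bc) / √[(a+b)(c+d)(a+c)(b+d)]
- lower = D − √[(p1−l1)² − 2φ(p1−l1)(u2−p2) + (u2−p2)²]
- upper = D + √[(u1−p1)² − 2φ(u1−p1)(p2−l2) + (p2−l2)²]

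**Equal sensitivities, 12/15 and 12/15.** The Wilson limits are 0.548 to 0.930, so p−l = 0.2519 and u−p = 0.1295. The squares sum to 0.0802 and the cross term is 2 × 0.2519 × 0.1295 = 0.0652.

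| Table | φ | Half-width |
|---|---|---|
| (12,0,0,3) | 36/36 = 1.00 | √(0.0802 − 0.0652) = 12.2 points |
| (11,1,1,2) | 21/36 = 0.58 | √(0.0802 − 0.0380) = 20.5 points |
| (10,2,2,1) | 6/36 = 0.17 | √(0.0802 − 0.0109) = 26.3 points |

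The separate estimates are identical in all three rows, yet the interval more than doubles in width. With the continuity correction to φ the half-widths are 16.9, 23.6 and 28.3.

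**80% versus 60%, 12/15 and 9/15.** The Wilson limits for 9/15 are 0.357 to 0.802, and the denominator of φ is √(12×3×9×6) = 44.09. Only two tables have non-negative association:

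| Table | φ | 95% interval for the 20-point difference |
|---|---|---|
| (9,3,0,3) | 27/44.09 = 0.61 | −0.5 to 39.3 |
| (8,4,1,2) | 12/44.09 = 0.27 | −7.7 to 44.2 |

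Both include zero, and both still do with the correction (−4.3 to 41.9; −10.6 to 46.3).

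**Other numbers of positives, equal 80% sensitivities.** 8/10 each gives ±16.7 to ±28.9 points; 24/30 each gives ±6.8 to ±18.7. The dependence on discordance remains at every size.

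**The case against.** Four points can be made for the plan as written.

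- **The difference is available by subtraction.** This stands. Pairing does not change the point difference, so it would be wrong to say that the plan yields no between-test difference or that objective 5 is wholly unanswerable. What is missing is its uncertainty.
- **Objective 5 states no hypothesis, so a descriptive comparison may be all that is meant.** This is a possible reading, and the documents make no superiority or equivalence claim. But a descriptive comparison in about 30 patients still needs a measure of precision.
- **The STARD commitment covers it.** As written it does not, because it names no comparative quantity or method.
- **The paired table can be built later from data already planned.** True, which limits the harm. Naming the method beforehand still avoids choosing it after results are known.

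Two stronger readings are tempting. A reader might infer that the unpaired tests are misapplied to paired data. They are not: they contrast SFN and non-SFN patients, who are independent groups. A reader might also infer that ignoring the pairing would reverse the conclusion about zero. With 80% versus 60%, whether the interval includes zero depends on discordance if all 30 patients are positive (−2.0 to 39.6 with 9–3 discordant pairs, 5.5 to 34.0 with 6–0). With 20 positives it does so only without the continuity correction (one table of three excludes zero, 2.2 to 36.9). At 15 or 10 positives every interval includes zero. The documents do not establish the 30-positive case, which would also leave specificity impossible to estimate.

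**Conclusion.** The concern holds as a gap in one secondary objective. The plan promises a within-patient comparison of WIWT with QST and SSR but specifies no measure of uncertainty for it. Under the assumed 15 reference-positives, equal observed sensitivities of 12/15 are compatible with anything from ±12 to ±26 points, and an observed 20-point gap does not exclude zero. These sizes rest on an assumed split, assumed agreement between tests, and literature sensitivities for WIWT and QST only; nothing comparable can be worked out for SSR. The conclusion that the interval depends on the cross-classification rests on none of these assumptions. The primary sensitivity and specificity of WIWT are unaffected. The plan should be changed, but the point does not undermine the study.

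**What to change.** Add to Statistical methods, separately for WIWT-QST and WIWT-SSR, in patients with both results and with their number stated:

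1. The cross-classified table of the two binary results, by reference status.
2. The paired difference in sensitivity (reference-positives) and in specificity (reference-negatives), each with a paired 95% confidence interval.
3. The AUC difference with a 95% interval by one correlated-curve method named in advance, for example DeLong.
4. A statement that these are estimates, not tests of superiority or equivalence.

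Keep the Mann-Whitney and t-tests as group contrasts.

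**Cost.** A few sentences, a few lines of analysis, and no new data. There is one prerequisite: the binary result and the score for QST and SSR must be fixed in Test methods before results are examined. The QST text gives an abnormality criterion only for vibration, and the SSR text gives reference values for latency and amplitude without a rule for combining them.

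**Limits.** The comparison will be reported as imprecise. The specificity and AUC differences need enough reference-negatives, and the documents conflict on whether there will be any. Definition and operationalization of variables describes tested patients as abnormal on more than one scale. Justification requires at least one scale for the SFN diagnosis, while Population and the inclusion criteria admit patients on specialist suspicion, with no scale result required. These passages should be reconciled. If no reference-negatives are enrolled, only the sensitivity difference can be reported.

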## Ethical considerations

The collected information will be confidential, and the participant's name will not appear in any record nor be disclosed, safeguarding confidentiality in accordance with Personal Data Protection Law No. 25.326. Written informed consent will be requested from all participants enrolled in the study.

